### 7.5.1 Descriptive Summaries by Visit

The change in score from Baseline will be analyzed as continuous variables. The composite score and the scores of each sub-scales at Baseline and the changes from Baseline will be summarized descriptively by visit and by treatment group using the observed cases (missing values will not be imputed).

The proportions (%) of subjects gaining/losing  $\geq 10$  points in score for the 4 pre-specified subscales, as well as the composite score, will be tabulated by visit and by treatment group using the observed cases (missing values will not be imputed).

Change in mean score from Baseline over time will be plotted by visit and by treatment group.

### 7.6 SENSITIVITY ANALYSES

### 7.6.1 Sensitivity analyses for the primary analysis

For the analyses of the primary endpoint, the Model for Repeated Measures (MRM) analysis does not require data imputation and uses only the observed data. Moreover, assuming that the missing data are MAR, the model yields valid results that are comparable to those obtained by applying MI under the MAR assumption.

To check the sensitivity of the results of the primary efficacy analysis to the MAR assumption, MI based on models compatible with Missing Not At Random (MNAR) missingness mechanisms will be used. Two approaches, using SAS' PROC MI, will be considered:

1. The "shift imputation" approach: for missing values at a particular visit, it will be assumed that their expected value is smaller (shifted) by a specified amount than for the observed responses (implying that the missing values are more likely corresponding to smaller changes vs. Baseline than the observed ones). Different values of the shift will be explored to investigate the sensitivity of the results. Scenarios with treatment-dependent shift values will also be explored. This approach can be applied to data with arbitrary missing data patterns.

2. The "pattern-mixture-model imputation" approach: missing values at Month 12 visit will be imputed by using the pattern-mixture-model restrictions. In particular, Neighbouring-Case Missing Value (NCMV) restrictions will be applied.

In addition to these two analyses, four analyses described by Miller et al. (2001) will be performed for further insight into the potential impact of missing data on the results:

- 1. the observed means from the active arm and the sham arm will be imputed to patients with missing data in the arm they were allocated to;
- 2. the observed means from the active arm and the sham arm will be imputed to patients with missing data in the opposite arm they were allocated to (a "cross-over" scheme);
- 3. the average of observed means from the active arm and the sham arm will be imputed to all patients with missing data;
- 4. the observed mean from the sham arm will be imputed to all patients with missing data.

Of note, these imputation techniques are known to induce potential bias, hence they will be used only for sensitivity purposes.

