### 11.1 Study Design

This is a randomized, double-masked, Sham controlled [REDACTED] study that will obtain evidence regarding the effects of multiple dose levels of Zimura™ in reducing the rate of GA growth over 12 months, when compared with the Sham control.

This [REDACTED] trial will provide evidence suggesting that a dose of Zimura™:

- Is not plausibly more efficacious than the Sham control, and should be discarded in its current formulation in this indication;
- Is plausibly more efficacious than the Sham control and should be evaluated definitively in a subsequent Phase 3 clinical trial; or
- Is more efficacious than the Sham control, with strength of evidence meeting the standard requirement of a 0.0125 one-sided false-positive error rate, adjusting for the multiple comparisons of 2 mg and 4 mg doses against the Sham control. A confirmatory trial likely would be required for regulatory approval.

Eligible subjects that consent to participate will be randomized to Zimura™ or Sham control in two parts of the trial. In Part 1, approximately 77 subjects are randomized to Zimura™ 1 mg vs Zimura™ 2 mg vs Sham control, in a 1:1:1 allocation. In Part 2, approximately 200 subjects are randomized to Zimura™ 2 mg vs Zimura™ 4 mg vs Sham control, in a 1:2:2 allocation. A total of approximately 277 subjects are to be randomized.

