### 7 EFFICACY EVALUATION

All efficacy analyses will be conducted for the ITT population. The primary and secondary endpoints will also be conducted for the PP population in a supportive manner.

The analyses will be based on comparisons of Zimura 2 mg vs. the Sham control, and Zimura 4 mg vs. Sham control. For the comparison of Zimura 2 mg vs. Sham control, the subjects randomized from Part 1 will be combined with the subjects randomized to from Part 2, where the analysis will be stratified by Part 1 vs. Part 2. The comparison of Zimura 4 mg vs. Sham control will only based on subjects randomized in Part 2.

The primary analysis will use the ITT population and will be based on a Model for Repeated Measures (MRM) to compare the treatment groups. This analysis provides valid estimates as long as the missing data mechanism fulfills the Missing at Random (MAR) assumption. However, sensitivity analyses (see Section 7.6) will be performed to assess the potential magnitude and direction of the impact of missing data. Although Zimura 1 mg dose is not of an interest, a

descriptive analysis for a treatment effect of Zimura 1 mg dose vs. Sham control will be conducted in a supportive manner.

The primary analysis **and the set of** for each of the two pairwise comparisons of an active dose of Zimura vs the Sham control is formally based on a three-category decision guideline. The decision guideline for this trial is based on whether the estimated mean reduction in rate of square root of GA area growth over 12 months for a dose of Zimura versus Sham control is less than 14%, is from 14% up to 24.5%, or is at least 24.5%. These numbers may be adjusted based on the final sample size and standard deviation.

- 1. If the estimated reduction in the rate of GA growth over 12 months for a dose of Zimura vs. Sham control is less than 14%, then this dose of Zimura is not plausibly more efficacious than the Sham control; its utility in this indication should be reconsidered.
- 2. If the estimated reduction in the rate of GA growth over 12 months for a dose of Zimura vs. Sham control is from 14% to up to 24.5%, then this dose of Zimura is plausibly more efficacious than the Sham control and should be evaluated in a subsequent Phase 3 clinical trial.

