### 7.6.2 Sensitivity analyses on the secondary endpoints

Sensitivity analyses on the secondary endpoints will also be performed using different methods of data imputation for missing values at a particular visit if applicable, namely 1) the "shift imputation" approach; and 2) the "pattern-mixture-model imputation" approach.

The latter approach can be applied to data with monotone missing data patterns. Hence, if necessary to apply the approach, the data will be transformed into the monotone patterns by considering the

longest uninterrupted sequences of the measurements for the subjects and/or excluding a few measurement visits from modelling, to increase the number of monotone patterns in the data. In case data are re-shaped, the primary analysis MRM model will be applied to the re-shaped data as well.

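### The shift imputation in SAP 7.6.1 moves missing GA growth in the favourable direction, and no upward shift for Zimura dropouts is specified

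*SAP*

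**What the plan says.** SAP 7.6.1 offers two multiple-imputation approaches under missing-not-at-random (MNAR) mechanisms to probe the MAR assumption of the primary analysis. The first is the shift approach. For a missing value, it assumes that "their expected value is smaller (shifted) by a specified amount than for the observed responses", and the SAP explains this as "implying that the missing values are more likely corresponding to smaller changes vs. Baseline than the observed ones". On size and allocation it says only "Different values of the shift will be explored to investigate the sensitivity of the results" and "Scenarios with treatment-dependent shift values will also be explored".

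The primary endpoint is the rate of change in GA over 12 months, analysed as the square root of area (SAP 7.2). Protocol 11.1 says the trial will study the effect of Zimura "in reducing the rate of GA growth over 12 months, when compared with the Sham control". The decision guideline in SAP 7 is likewise framed as a percentage reduction in growth, with cuts at 14% and 24.5%.

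SAP 7.6.1 adds four single-mean imputations. In the cross-over version each dropout receives the opposite arm's mean, and in the Sham-mean version every dropout receives the Sham mean. Of these techniques the SAP says that "these imputation techniques are known to induce potential bias, hence they will be used only for sensitivity purposes".

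SAP 7.6.2 reuses the shift approach for the two visual acuity endpoints.

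**The concern.** For GA a larger change from Baseline is the worse outcome. A sensitivity analysis for missing data should ask what happens if the unseen subjects, especially those on active treatment, did worse than MAR predicts. The only direction written down asks what happens if they did better. The same direction is adverse for letter scores, where a smaller value is worse, so one sentence cannot serve both endpoints, and nothing in the SAP reverses it for GA.

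What is at stake is the robustness claim. A positive GA result could be reported as having survived an MNAR analysis whose default setting cannot weaken it unless Sham loses more subjects. The scenarios that could weaken it are left to be chosen later, although Protocol 11.6.1 assigns the specification of imputation methods to the SAP, before unmasking.

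**Working it through.** **Inputs from the documents.** Cuts of 14% and 24.5%, one-sided 0.0125 per comparison, a true reduction of 28%, and stated chances of 63% (significance), 90% (carried forward at 28%) and 10% (carried forward under no effect), all from Protocol 11.3. The direction of shift is from SAP 7.6.1.

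**Assumptions.** The documents give no dropout rate, shift size or standard deviation. For illustration, Sham growth is set to 100 and Zimura to 72. Missing fractions range from 10% to 25%, and the shift is 28 points, that is, 28% of Sham growth. Before any shift, dropouts have the same mean as the observed subjects in their arm.

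**Step 1: scale.** The cuts imply the planned standard error (SE) of the reduction: 24.5/2.2414 = 10.9 and 14/1.2816 = 10.9 percentage points. With SE 10.93:
- significance at 28%: 1 − Φ((24.5 − 28)/10.93) = 62.6% (stated 63%)
- carried forward at 28%: 1 − Φ((14 − 28)/10.93) = 90.0% (stated 90%)
- carried forward under no effect: 1 − Φ(14/10.93) = 10.0% (stated 10%)

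The plan's figures reproduce. This step only fixes the scale.

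**Step 2: effect of a shift.** With missing fractions mZ and mS and signed shifts dZ and dS:

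Reduction = 1 − (72 + mZ·dZ)/(100 + mS·dS)

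| Scenario | mZ / mS | Zimura / Sham mean | Reduction |
|---|---|---|---|
| Common, −28 (as written) | 20% / 10% | 66.4 / 97.2 | 31.7% |
| Common, +28 | 20% / 10% | 77.6 / 102.8 | 24.5% |
| Zimura only, −28 | 20% / 10% | 66.4 / 100 | 33.6% |
| Zimura only, +28 | 20% / 10% | 77.6 / 100 | 22.4% |
| Common, −28 | 20% / 20% | 66.4 / 94.4 | 29.7% (difference 28.0, unchanged) |
| Sham only, −28 | mS = 10% | 72 / 97.2 | 25.9% |
| Sham only, −28 | mS = 20% | 72 / 94.4 | 23.7% |
| Common, −28 | 10% / 20% | 69.2 / 94.4 | 26.7% |
| Common, +28 | 10% / 20% | 74.8 / 105.6 | 29.2% |

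A downward shift weakens the result only in the Sham-only rows and where Sham loses more subjects. The last row shows that reversing the sign of a common shift is not a remedy in itself.

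**Step 3: what the planned mean imputations reach.**
- Cross-over: 74.8/97.2 gives 23.0% at 10% missing per arm; 77.6/94.4 gives 17.8% at 20%.
- Sham mean: 74.8/100 gives 25.2% at 10%; 77.6/100 gives 22.4% at 20%.

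Both give Zimura dropouts the Sham mean, an upward move of 28 points and never more.

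**Step 4: tipping shift.** With Sham at MAR and the planned SE held, the Zimura-only upward shift that takes 28% down to the 24.5% cut is (28 − 24.5)/mZ:
- 35 points at 10% missing
- 23.3 at 15%
- 17.5 at 20%
- 14 at 25%

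It equals 28 at mZ = 3.5/28 = 12.5%. Below that fraction, the Sham-mean imputation stops short of the tipping point.

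**The case against.** Four arguments can be made for leaving the plan alone.

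*Treatment-dependent shifts already allow an adverse case.* The primary test is a difference between arms. At equal dropout, a Sham-only downward shift gives the same difference as a Zimura-only upward shift of the same size: at 20% missing and 28 points, 94.4 − 72 = 22.4 and 100 − 77.6 = 22.4. This is correct, so the written direction does not make an adverse result impossible. But the SAP names no arm, size or grid, and making Sham dropouts do better is an indirect way to ask whether Zimura dropouts did worse.

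*Cross-over imputation is already harsh.* At equal dropout m it removes 56m points from the difference. It falls below the 24.5% cut at about 6% missing per arm on the difference scale (3.5/56) or 7% on the ratio scale. So the plan does contain an adverse scenario. It is, however, one fixed scenario built by filling in a mean. It adds no imputation uncertainty and gives no tipping point, and the SAP itself flags it as potentially biased.

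*The tipping figures are soft.* Under the Hochberg procedure (SAP 7.1), if both doses reach one-sided 0.025, the limit is 1.96 × 10.93 = 21.4, and the tipping shift at 20% missing becomes (28 − 21.4)/0.20 = 33. If instead 80 per arm means complete data and the missing 20% contribute nothing, the SE is 10.93/√0.8 = 12.2, the cut is 2.2414 × 12.2 = 27.4, and the shift is (28 − 27.4)/0.20 = 3. SAP 7 also allows the cuts to be adjusted. This stands: 17.5 is an illustration within a range of roughly 3 to 33.

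*It is only a sensitivity analysis.* This also stands, and it limits the weight of the point. It does not make the stated direction right.

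**Conclusion.** The concern holds. The one direction written for the primary endpoint's shift analysis is favourable for the imputed subject's GA outcome, and no upward shift for Zimura dropouts is specified. Whether this flatters the treatment effect depends on dropout. It does if Zimura loses more subjects. With equal dropout a common shift leaves the difference unchanged and slightly raises the percentage reduction. If Sham loses more, the shift as written is conservative. Under the illustrative assumptions, the sign of a Zimura-only shift separates 33.6% from 22.4%, on opposite sides of the 24.5% cut. Those sizes rest on assumed dropout, shift and effect; the conclusion about direction rests on the text alone. The primary estimate, its test and the alpha allocation are not affected, so this should be corrected before unmasking but does not undermine the primary analysis.

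**What to change.** In SAP 7.6.1 and 7.6.2, before unmasking:

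- State the adverse direction per endpoint: larger growth for missing GA values, fewer letters for missing visual acuity values.
- Pre-specify a grid of shifts by arm for GA. Include Zimura-only upward shifts with Sham at MAR, and extend the grid beyond the Sham mean.
- Report, for each dose, the shift at which significance is lost, using the SE from the imputed data and the Hochberg procedure in place of the planning cut of 24.5%.
- Do not simply reverse the sign of a common shift, for the reason shown in the working.

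The cost is a short paragraph, a grid and extra runs of the PROC MI program already planned. No new data are needed and the primary analysis does not change.

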### 3.2.1 Intention-To-Treat (ITT) Population

The intention-to-treat population (ITT) will consist of all randomized subjects who received at least one dose of study drug, irrespective of the dose actually received. Subjects will be analyzed in the treatment group assigned at randomization. Subjects will be included in a particular analysis, for a particular population, if relevant data is available for analysis (e.g., the primary analysis will require both Baseline and at least one post-Baseline GA measurement, to calculate a change score).

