### 7.2 ANALYSIS OF PRIMARY EFFICACY ENDPOINT

The primary efficacy endpoint is mean rate of change in GA over 12 months measured by fundus autofluorescence (FAF) at three time points: Baseline, Month 6, and Month 12. To eliminate the dependency of GA growth rates on the Baseline lesion size (Feuer et al., 2013), instead of using the observed GA area measurement, the square root of the GA area will be used in the analysis.

For analyses of the primary endpoint, a Mixed-Effects Repeated Measures (MMRM) model will be used to assess the differences between the treatment groups in rate of change of GA area over 12 months. Two separate models will be fitted for comparing Zimura 4 mg vs. Sham control, and Zimura 2 mg vs. Sham control. Both models will be fitted by using restricted maximum likelihood (REML) and include Baseline VA (< 50 letters vs.  $\geq 50$  letters), size of the Baseline GA (< 4 disc area vs.  $\geq$  4 disc area), and pattern of FAF at the junctional zone of GA (none/focal vs. banded/diffuse) as used in the randomization as covariates. For Zimura 2 mg vs. Sham control model, fixed effects will include treatment, visit, part (Part 1 vs. Part 2), the Baseline VA (< 50 letters vs.  $\geq$  50 letters), size of the Baseline GA (< 4 disc area vs.  $\geq$  4 disc area), pattern of FAF at the junction zone of GA (none/focal vs. banded/diffuse), treatment by visit interaction, and the stratification factors by visit interactions. For Zimura 4 mg vs. Sham control model, the same fixed effects will be used excluding part (Part 1 vs. Part 2). An unstructured (co)variance structure will be used to model the within-subject errors. If this analysis fails to converge, alternative structures (e.g., heterogeneous autoregressive or heterogeneous compound symmetry, in this order) will be considered. The Kenward-Roger approximation will be used to estimate denominator degrees of freedom. The test of the mean rate of change over 12 months will be assessed by testing the appropriate contrast of the model parameter estimates.

In addition to the analyses described above, a similar analysis will be conducted using the observed GA area measurement.

The analyses described above will also be repeated in a supportive manner for the PP population.

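### With GA measured at only three visits, the NCMV analysis planned as an MNAR check makes the MAR assumption for every subject in the primary analysis set who lacks Month 12

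*SAP*

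**What the plan says.** The primary analysis (SAP 7 and 7.2) is a repeated-measures model fitted by REML to observed data, valid under MAR. GA enters it "at three time points: Baseline, Month 6, and Month 12". SAP 3.2.1 adds that "the primary analysis will require both Baseline and at least one post-Baseline GA measurement".

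To test the MAR assumption, SAP 7.6.1 states that "MI based on models compatible with Missing Not At Random (MNAR) missingness mechanisms will be used" and names two approaches:

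1. Shift imputation. For missing values "it will be assumed that their expected value is smaller (shifted) by a specified amount than for the observed responses", which the SAP explains as smaller changes from Baseline. It adds that "Scenarios with treatment-dependent shift values will also be explored".
2. Pattern-mixture imputation. Here "missing values at Month 12 visit will be imputed by using the pattern-mixture-model restrictions", and "Neighbouring-Case Missing Value (NCMV) restrictions will be applied".

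Four single mean-imputation analyses follow, and the SAP itself warns that they may be biased. For the secondary endpoints, SAP 7.6.2 lists the same two multiple-imputation approaches and says of the second: "The latter approach can be applied to data with monotone missing data patterns".

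**The concern.** NCMV can depart from MAR when dropout occurs at several different visits, because it borrows from the adjacent dropout pattern instead of from everyone still observed. The primary endpoint has only two post-Baseline visits, and the primary analysis set excludes subjects with neither. That leaves no adjacent pattern other than the completers, who are also the MAR donors.

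Item 2 is nevertheless presented as a test of MAR. A report that NCMV agrees with the MMRM could be read as robustness to MNAR, although the agreement is built in.

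That puts more weight on item 1, whose wording covers one direction only. For GA, a smaller change means slower growth, which is the favourable outcome. No multiple-imputation scenario names faster growth in active-arm subjects who are missing.

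**Working it through.** **Which patterns can occur.** Protocol 10.2 schedules FAF at Screening, Month 6, Month 12, Month 18 and early withdrawal. The SAP covers one-year data only (SAP 1). An early-withdrawal image either fills a visit window or the visit is missing (SAP 3.4.2). With monotone missingness:

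| Pattern | Observed | In the primary analysis set? |
|---|---|---|
| P1 | Baseline | No (SAP 3.2.1) |
| P2 | Baseline, Month 6 | Yes |
| P3 | Baseline, Month 6, Month 12 | Yes |

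**Donors for Month 12 given Baseline and Month 6, in P2.**

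- NCMV uses the pattern whose last observed visit is Month 12, which is P3.
- MAR with monotone data uses all patterns with Month 12 observed, which is again P3.

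The two restrictions are the same. SAP 7.6.1 also says that the repeated-measures model and MAR-based imputation give comparable results, so on the SAP's own account item 2 should reproduce the primary analysis.

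**Numerical confirmation.** Square-root GA data were simulated with MNAR dropout (all parameters assumed). The mean change to Month 12 was:

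| Set | NCMV | MAR (likelihood fit) |
|---|---|---|
| Primary set, n = 18,126, 3,347 without Month 12 | 0.327259 | 0.327259 |
| About trial size, n = 100, 23 without Month 12 | 0.321542 | 0.321542 |
| Baseline-only added, n = 20,000, 1,950 of them Baseline-only | 0.334486 | 0.326356 |
| Primary set, some subjects with Month 6 missing and Month 12 present | 0.329074 | 0.328987 |

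In the third row the departure comes from the Month 6 step, where NCMV borrows from P2 and MAR from P2 and P3 together. Month 12 given Month 6 remains MAR. The 0.000087 gap in the fourth row arises because the likelihood also uses the Baseline + Month 12 subjects. It is not an MNAR departure.

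**Scale, from the plan's own figures (protocol 11.3).**

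- 10% chance under no effect of passing 14%: SE = 14/1.2816 = 10.92 points.
- One-sided 0.0125 at 24.5%: SE = 24.5/2.2414 = 10.93 points.
- Check: Φ((28 − 24.5)/10.92) = 62.6%, against the stated 63%.
- With 80 per arm, the SD of 12-month growth = 0.1093 × √40 = 0.69 of the sham mean.

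**Illustration in percentage points of reduction.** The documents give no dropout rate, so these inputs are assumed:

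- true reduction 28%;
- Month 6–Month 12 growth correlation 0.7 or 0.85;
- faster growers more likely to leave, logit slope 0.5 or 1.0 per SD of Month 12 growth;
- missing Month 12 (sham/active) 5/5, 5/10, 10/10, 8/15, 10/20 or 20/20%.

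That makes 2 × 2 × 6 = 24 scenarios, with 1,000,000 subjects per arm. Three of them:

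| Missing sham/active | Correlation, slope | MAR | NCMV | Reference-based |
|---|---|---|---|---|
| 5/5% | 0.85, 0.5 | 28.08 | 28.08 | 27.38 |
| 8/15% | 0.7, 0.5 | 29.60 | 29.60 | 27.28 |
| 10/20% | 0.7, 1.0 | 32.18 | 32.18 | 28.63 |

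Over all 24, NCMV minus MAR was 0.00, MAR was off the truth by 0.1 to 4.2 points, and reference-based imputation moved 0.7 to 3.6 points from MAR. At trial size (80 per arm, 2,000 replicates, 20 imputations, common draws) the largest difference between MAR and NCMV was 0.

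**If Baseline-only subjects were entered** (correlation 0.7, slope 1.0, P2 at 8/15%):

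| Baseline-only sham/active | MAR | NCMV | Difference |
|---|---|---|---|
| 2/2% | 31.40 | 31.30 | 0.10 |
| 10/10% | 33.11 | 32.58 | 0.53 |
| 2/5% | 33.36 | 32.56 | 0.80 |

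**The case against.** **The analysis set is not fixed for the imputations.** The post-Baseline requirement in SAP 3.2.1 is given as an example tied to the primary analysis, and SAP 7 runs all efficacy analyses on the ITT population. Section 7.6.1 does not exclude Baseline-only subjects. If they entered, NCMV would depart from MAR, and in the three cases above towards the true value. This stands as a limit on the finding. But the SAP nowhere says they are added, the departure is at most 0.8 points in those cases, and the Month 12 step is still MAR.

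**The 0.00 result is true by construction.** Correct. The simulations illustrate the algebra; they do not estimate how much bias to expect.

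**Other checks remain.** Also correct. Treatment-dependent shifts are a genuine MNAR tool, and even a downward shift works against the drug if applied to sham alone. With 8% missing sham and a half-SD shift (0.345), the sham mean becomes 1 − 0.08 × 0.345 = 0.9724 and the reduction becomes 1 − 0.72/0.9724 = 26.0%, down 2.0 points. The second and fourth single mean imputations give sham means to missing active subjects. What remains is that no multiple imputation is worded to cover faster growth in missing active-arm subjects, and the single imputations carry the SAP's own warning of bias.

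**Relabelling would do, and the replacement is partly preference.** In the 5/5% case reference-based imputation (27.38) lies further from 28.0 than MAR does (28.08). That is fair, but a sensitivity analysis is meant to change the assumption, not to come closest in one scenario. Relabelling would prevent the misreading but would leave one informative multiple-imputation check where the SAP intends two.

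**Conclusion.** The concern holds. For the primary endpoint, within the primary analysis set, item 2 of SAP 7.6.1 is not an MNAR analysis. It makes the MAR assumption for every subject without Month 12 and cannot test it. The conclusion follows from three visits, the post-Baseline requirement and the definition of NCMV; it does not depend on any assumed dropout rate. The difference from MAR is nil for these subjects. Only entering Baseline-only subjects and imputing their Month 6 value by NCMV creates an MNAR departure (0.1 to 0.8 points in the cases tried).

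The size of the consequence is modest. Against a standard error near 10.9 points, the illustrated MAR error of 0.1 to 4.2 points is not dominant, and it rests on assumed dropout. The plan also keeps a real MNAR analysis in the shift approach. The change should be made because a planned robustness check can show nothing and the remaining multiple-imputation check is worded in the favourable direction. The finding does not extend to monthly visual acuity, where NCMV and MAR can differ.

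**What to change.** In SAP 7.6.1, for the primary endpoint:

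- Replace item 2 with reference-based multiple imputation, in which active-arm subjects missing Month 12 are given sham-arm growth after their last FAF.
- In item 1, allow shifts in both directions, and name scenarios with larger growth for missing active-arm values.
- For clarity, state whether Baseline-only subjects enter the imputation analyses and how a subject with Month 6 missing and Month 12 observed is handled.

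Keep NCMV in SAP 7.6.2 for the monthly visual acuity endpoints.

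The cost is SAP wording and a standard imputation program, with no new data. The sensitivity result may be less favourable. The primary estimate, alpha and decision categories do not change.
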